#### SPM Analysis

Statistical parametric mapping software (SPM2, Wellcome Department of Imaging Neuroscience in the Institute of Neurology at University College London) implemented in Matlab 6.5 (Mathworks Inc., Sherborn, MA) will be used for voxel-based statistical analysis. Each scan will be transformed into sterotactic space by normalizing to a template image. The images are then smoothed using a Gaussian kernel (8x8x8 FWHM).

For outcome measures for cardiac FDG, using the CT as guide, the ascending aorta, aortic arch and carotid arteries will be delineated. For aorta, ROIs will be drawn every 3 mm around the artery along the aorta, starting 1 cm distal to aortic valve (to avoid spillover from the heart) and ending after the takeoff of the left subclavian artery. For carotid arteries, serial regions of interest will be drawn around each carotid, starting 2 cm below carotid artery bifurcation and extending 2 cm into internal carotid artery. The mean and maximum standardized uptake value [SUV, decay-corrected tissue concentration of [18]F-FDG (in Bq/mL) divided by the injected dose per body weight (Bq/g)] on co-registered PET images will be determined for each ROI, and will be averaged along each artery. Background (blood) activity will be determined in 5 ROIs separated 3 mm apart drawn around superior vena cava (for aorta) and ipsilateral jugular vein (for carotid artery). Target to background ratio (TBR) will be calculated by dividing the average SUVmax by background activity. For each subject, the artery with the highest TBRmax will be selected as the index vessel for all analyses.

### **Sample Size Calculation**

Power calculations were conducted by a statistician and Co-I, [name]. Preliminary data from 6 individuals with PTSD and 8 trauma-exposed controls revealed robustly higher [C]PBR28 VT values globally (21.5% higher; d=1.02) and regionally (17.3-30.1% higher; d's=0.83-1.15) in PTSD vs. controls.}} Assuming a two-sided analysis of covariance (ANCOVA) with  $\alpha$ =0.05, recruitment of 40 trauma-exposed controls and 40 individuals with PTSD (quartiles 3-4) will provide greater than 94.2% statistical power to detect effect sizes as small as d=0.80. This translates into minimum detectable differences between controls and individuals with PTSD of 15.0%. To examine relations between continuous measures of global and regional [11C]PBR28 V1 values, and measures of post-traumatic threat and loss symptoms, and neurocognitive functioning, preliminary data from 5 individuals with moderate-or-greater severity of MDD symptoms revealed a strong association between global [11C]PBR28  $V_{T}$  values and severity of loss/anhedonic symptoms (r=0.82). Further, preliminary data from 23 individuals revealed that global [ $^{11}$ C]PBR28 VT values correlated significantly with measures of learning and memory (r= -0.47) and working memory (r= -0.39). Thus, assuming a two-sided linear multiple regression model with  $\alpha$ =0.01 (0.05/5 dependent variables: dot probe and PRT scores, CAPS-5-assessed threat and loss symptoms, global cognition) and conservative overall model effect size (R^2) of .25, and up to 10 predictors, an n of 80 will provide 99.2% statistical power to detect this magnitude effect. Our previous study in 8 healthy controls revealed robust LPS-induced increases in [ $^{11}$ C]PBR28 VT values ranging in magnitude from 31% to 63%(13). We have preliminary data indicating an overall 8.8% difference (d=0.38)in global [C]PBR28 VT values between 2 individuals with PTSD and 2 matched trauma-exposed controls. Thus, assuming a minimum 8.0% differential increase in LPS-induced  $[^{11}C]PBR28 V_T$  values in the PTSD group relative to trauma-exposed controls(16),  $\alpha$ =0.05, correlation among repeated measures=0.50, and nonsphericity correction  $\varepsilon = 1$ , recruitment of 40 individuals with PTSD and 40 trauma-exposed controls will provide greater than 91.9% statistical power to detect this magnitude differential effect size.

MRI

MR imaging will be performed on a Prismab MRI with a circularly-polarized head coil located at the Anlyan Center, a member of the research team will accompany the subject to the MRRC and will stay for the MRI exam. MR acquisition will be a Sag 3D magnetization-prepared rapid gradient-echo (MPRAGE) sequence with 3.34 ms echo time, 2,500 ms repetition time, 1,000 ms inversion time, 7degree flip angle, and 180 Hz/pixel bandwidth. The image dimensions will be 256 x 256 x 176 and pixel size is 0.98 x 0.98 x 1.0 mm.

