In Aim 1, we will determine whether individuals with PTSD have higher levels of activated microglia compared to trauma-exposed control subjects as measured with [C]PBR28 PET brain imaging. Eighty subjects (n=40 with a primary diagnosis of PTSD; n=40 trauma-exposed controls) will participate in a [C]PBR28 PET scan to assess baseline levels of activated microglia. We will perform clinical assessments and measure cytokine levels, mood, anxiety and neurocognitive function on PET scan day. *Based on our preliminary data, we hypothesize that individuals with PTSD will have higher levels of neuroinflammation compared to trauma-exposed healthy controls, particularly in the amygdala, hippocampus, ventral striatum and frontal cortex, and that higher levels of neuroinflammation will be associated with greater severity of mood and anxiety symptoms and neurocognitive dysfunction.* 

In Aim 2, we will use our novel neuroinflammation "stress test" to determine whether individuals with PTSD vs. trauma-exposed controls have a dysfunctional neuroinflammatory response to systemic administration of LPS. The same subjects from Aim 1 will be administered LPS 3 h prior to a second [C]PBR28 PET scan on the same day, consistent with our established paradigm(13). Cytokine and cortisol levels, mood and anxiety symptoms, and neurocognitive function will be assessed pre- and post-LPS administration. *We hypothesize based on preclinical studies(16) that, compared to controls, individuals with PTSD will have an exacerbated neuroimmune response to LPS evidenced by greater increases in activated microglia. We further expect that greater LPS-induced increases in activated microglia will be associated with greater increases in cortisol levels, mood and anxiety symptoms, and reductions in neurocognitive function.* 

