**Study Hold Criteria:** The following is criteria that will be used to halt enrollment or further participation of enrolled subjects pending safety review based on: the number of adverse events considered possibly probably or definitely related to endotoxin administration.  $\geq 2$  grade 3 adverse events, > 1 grade 4 clinical or laboratory adverse event, or 1 grade 5 adverse event [

13. **Statistical Considerations:** Describe the statistical analyses that support the study design. Frequency distributions and descriptive statistics for all variables will be computed prior to conducting analyses. Should Shapiro-Wilk normality tests indicate non-normality for any continuous variable, we will compute necessary

# Page 27 of 45

data transformations (e.g., logarithmic base 10) prior to conducting analyses. Preliminary data revealed large (i.e., r's>.80) magnitude correlations among [C]PBR28  $V_{T}$  values in all of the brain regions assessed. Thus, we will conduct a principal components analysis with oblique (promax) rotation of [C]PBR28  $V_{T}$  values in all brain regions assessed to calculate a global composite measure of [C]PBR28  $V_{T}$  values.

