A univariate ANCOVA will be used to compare global [C]PBR28  $V_{T}$  values between trauma-exposed controls and individuals with PTSD. Group (Control vs. PTSD) and rs6971 genotype on the TSPO gene will be entered as fixed factors(102), variables that differ between Control and PTSD groups as additional fixed factors (categorical variables *such as major depressive disorder*) or covariates (continuous variables *such as time since index trauma*), and global [C]PBR28  $V_{T}$  values as the dependent variable. A post-hoc multivariate ANCOVA will be conducted with the same independent variables and [C]PBR28  $V_{T}$  values in individual brain regions entered as dependent variables;  $\alpha$  will be set to 0.005 (0.05/10 brain regions) in this analysis to control for Type I error. To evaluate the relation between continuously distributed global [C]PBR28  $V_{T}$  values and measures of post-traumatic threat and loss symptoms, and neurocognitive functioning, we will conduct a linear regression model using Mplus version 7.31(124). In this analysis, global [C]PBR28  $V_{T}$  values will be modeled as the independent variable, and continuously-distributed scores on objective endophenotypic measures of threat and loss symptoms, and neurocognitive functioning, and clinician interview-based measures of threat and loss symptoms will be modeled as dependent variables. Should correlation analyses reveal large magnitude associations (i.e.,  $r \ge 0.70$ ) among variables will be modeled and analyzed as latent variables.

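### The 94.2% power stated for Aim 1 belongs to the global VT test at alpha 0.05; the regional tests run at alpha 0.005, where power at d=0.80 is about 75% and is not stated

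*Combined protocol and SAP*

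**What the plan says.** The Sample Size Calculation (Section I, item 4) reports the pilot difference between 6 subjects with PTSD and 8 controls first for the whole brain, "globally (21.5% higher; d=1.02", and then for individual regions, with d from 0.83 to 1.15. The power statement comes next. It opens "Assuming a two-sided analysis of covariance (ANCOVA) with" alpha 0.05, is based on "recruitment of 40 trauma-exposed controls and 40 individuals with PTSD", and claims that this "will provide greater than 94.2% statistical power to detect effect sizes as small as d=0.80". It names neither global nor regional VT.

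Item 13, Statistical Considerations, separates the two. The main group comparison is one univariate ANCOVA on global VT, with group and TSPO genotype as factors. The regional comparison is a post-hoc multivariate ANCOVA, for which alpha "will be set to 0.005 (0.05/10 brain regions) in this analysis to control for Type I error". Just before this, the plan notes: "Preliminary data revealed large (i.e., r's>.80) magnitude correlations among" regional VT values. It gives this as the reason for forming a global composite by principal components.

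The regions are described in three ways. The Aim 1 hypothesis in the Statement of Purpose expects higher levels "particularly in the amygdala, hippocampus, ventral striatum and frontal cortex" (four regions). MRI-Based ROI Definition lists six primary regions and leaves the others for post hoc study. Item 13 divides alpha by ten.

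**The concern.** The planning effect of 0.80 lies just under the smallest regional pilot effect (0.83) and well under the global one (1.02). With no scope given, a reader will naturally take the 94.2% to cover the regions as well. The same section does use a multiplicity-adjusted alpha (0.05/5 = 0.01) for its next calculation, the symptom and cognition regressions, so the reader has reason to expect that adjustment was handled where it applied.

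What is at stake is how a negative finding in a named region is read. At 94.2% power a true d of 0.80 is missed about one time in 17 (1 - 0.942 = 0.058). At about 75% it is missed about one time in four. A non-significant amygdala or hippocampus result would then be weaker evidence of no effect than the sample-size section suggests.

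**Working it through.** **Inputs.** From the Sample Size Calculation: 40 per group, two-sided test, alpha 0.05, d=0.80, regional pilot d from 0.83 to 1.15, global pilot d=1.02. From item 13: regional alpha 0.05/10 = 0.005 and correlations between regions above 0.80.

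**Method.** Two-group comparison by noncentral t with df = 2 × 40 - 2 = 78 and noncentrality d × √(40/2) = d × √20. Power is the probability that this variable exceeds the two-sided critical value (the opposite tail is negligible).

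**Step 1: reproduce the plan's figure.** At d=0.80 the noncentrality is 0.80 × 4.472 = 3.578. The critical value at alpha 0.05 is 1.991. Power is 94.2%, as printed. Spending up to 10 degrees of freedom on covariates gives 94.1% to 94.2%. A one-sided test would give 97.1%, so the printed figure is two-sided. It fits the global ANCOVA.

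**Step 2: the same calculation at the regional alpha.** At alpha 0.005 the critical value rises to 2.889.

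| True d | Power at alpha 0.05 | Power at alpha 0.005 (one region) |
|---|---|---|
| 0.80 (planning value) | 94.2% | 75.2% |
| 0.83 (smallest regional pilot value) | 95.6% | 79.1% |
| 1.02 (global pilot value) | 99.5% | 94.9% |
| 1.15 (largest regional pilot value) | 99.9% | 98.6% |

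At d=0.80 the regional figure is 94.2 - 75.2 = 19 points below the printed one (74.8% to 75.2% with up to 10 covariate degrees of freedom). With 40 per group and alpha 0.005, 80% power needs d of about 0.84 and 94.2% needs d of about 1.00. Keeping 94.2% at d=0.80 would take 62 per group.

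**Step 3: how conservative 0.05/10 is.** I simulated ten equally correlated test statistics under no effect. The plan gives only a lower bound on the correlation and does not say whether it is adjusted for genotype. That matters because the plan reports a roughly two-fold VT difference between high and medium binders, which can raise unadjusted correlations, while the planned tests adjust for genotype. I therefore show a range that starts below 0.80.

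| Assumed r | Familywise error at 0.005 per test | Per-test alpha that holds 5% | Power per region at d=0.80 |
|---|---|---|---|
| 0.5 | about 3.9% | about 0.0066 | about 78% |
| 0.8 | about 2.4% | about 0.012 | about 84% |
| 0.9 | about 1.7% | about 0.017 | about 87% |

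The last column is for a single-step max-T threshold. A step-down version does at least as well.

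**The case against.** The strongest reply is that nothing has been miscalculated. The main Aim 1 test is one global ANCOVA, alpha 0.05 is right for it, and alpha appears in the same sentence as the power. The regional analysis is labelled post hoc, and it is normal to power the main test only. This stands: a reader might infer that the 94.2% is an error, and the documents do not support that. It does not settle the point, because the Aim 1 hypothesis names four regions and the ROI section calls six regions primary. A named hypothesis in primary regions merits a stated power.

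A reader might also infer that the plan overlooks the correlation between regions, or that Bonferroni gains nothing. Neither holds. The plan uses the correlation to justify the global composite, and Bonferroni controls familywise error under any dependence without modelling. The issue is lost efficiency in the regional threshold only, and at r=0.5 the gain from max-T is about 3 points.

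Third, 75% is the value at d=0.80, below every regional pilot effect; over the pilot range power is 79% to 99%. That is fair, but the pilot values come from 6 and 8 subjects, and 0.80 is the plan's own planning value.

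Fourth, a miss rate of one in four is per region. It is not the chance that every region is negative. If all ten regions truly had d=0.80, at least one would reach 0.005 in about 93% of simulated trials at r=0.8 (about 89% at r=0.9 and 99% at r=0.5). The concern is therefore about conclusions on particular regions.

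**Conclusion.** The point holds as a matter of scope and efficiency. The 94.2% at d=0.80 is correct for the global VT test and does not carry over to the regional tests, where power per region at the planned alpha is about 75% at d=0.80 and 79% at the smallest regional pilot effect. The plan states no regional power. The regional threshold is valid but conservative, and a correlation-aware procedure would recover roughly 3 to 12 points at d=0.80 (78% to 87% against 75%) for r between 0.5 and 0.9.

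The power figures assume no dropout, that d already reflects residual variance after adjustment, and that covariates cost degrees of freedom but do not otherwise weaken the group contrast. The familywise figures also assume equal correlation among ten tests. They should not be carried over to the regional tests of LPS-induced change in Aim 2: the same 0.005 applies there, but the documents give no between-region correlation for those changes.

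**What to change.** 1. In item 13, replace the fixed 0.05/10 rule for the Aim 1 regional comparison with a step-down familywise procedure on the same genotype-adjusted ANCOVA. Westfall-Young max-T by residual permutation, with each permutation applied to all regions together, uses whatever correlation the data have. At minimum use Holm, which needs no correlation assumption and never rejects less than Bonferroni.
2. In the Sample Size Calculation, say that 94.2% at d=0.80 is for the global VT ANCOVA at alpha 0.05. Add the regional power for the procedure adopted: about 75% at d=0.80 if 0.005 is kept, or the max-T figure with its assumed correlation.
3. Make the Aim 1 hypothesis, the ROI section and item 13 agree on the number and status of the regions: four hypothesised, six primary, divisor of ten. The hippocampus is hypothesised but is not on the primary list.
4. State whether the correlations above 0.80 are adjusted for genotype.

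The cost is some wording and a short permutation script, with slightly less simple reporting of adjusted p-values. No subjects or scans are added. The stated regional power will look less favourable than the 94.2% now printed.

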## d) Higher levels of activated microglia are associated with

**neurocognitive dysfunction**. Preliminary data (n=23) were analyzed to evaluate the relation between global [C]PBR28 *V*T values and performance on a comprehensive neurocognitive test battery developed by Cogstate (www.cogstate.com), which assesses processing speed, visual attention, verbal and visual learning and memory, visual working memory, and spatial problem-solving(104, 105). On average, this sample was 29.7 years old (SD=7.3, range=19-44), predominantly male (65.2%), ethnically diverse (43.5% African American, 30.4% Caucasian, 21.7% Hispanic, 4.3% Hispanic), and comprised of n=13 [56.5%] healthy controls, n=7 [30.4%] individuals with alcohol dependence and 3 [13.1%] with PTSD. Partial correlations adjusted for the rs6971 polymorphism on the TSPO gene and psychiatric disorder revealed that higher global [C]PBR28 *V*T values were associated with significantly worse performance on measures of learning and memory (r= -0.47, p=0.021), and working memory (r= -0.39, p=0.034). These results suggest that higher levels of activated microglia are associated with decrements in learning and memory, as well as working memory. In Aim 1, we will build on these preliminary results to determine how baseline levels of activated microglia contribute to neurocognitive dysfunction in PTSD.

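### The 99.2% power for the symptom and cognition regressions does not match its stated inputs: an overall R² of .25 gives 81%, and about 99% needs .25 to be the partial R² of V_T alone

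*Combined protocol and SAP*

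**What the plan says.** The Sample Size Calculation (Section I, Research Plan) sets out the power for relating V_T to symptoms and cognition by "assuming a two-sided linear multiple regression model with" alpha 0.01. The alpha is derived as "0.05/5 dependent variables: dot probe and PRT scores, CAPS-5-assessed threat and loss symptoms, global cognition". The effect is described as a "and conservative overall model effect size", an R² of .25. The result is "and up to 10 predictors, an n of 80 will provide 99.2% statistical power to detect this magnitude effect".

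The paragraph leads up to this with pilot correlations: r = 0.82 between V_T and loss/anhedonic symptoms in 5 people with MDD, and two values from 23 people. Preliminary studies, item d, gives those two with p-values: "r= -0.47, p=0.021), and working memory (r= -0.39, p=0.034". It describes them as partial correlations adjusted for rs6971 genotype and psychiatric disorder.

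Section 13 (Statistical Considerations) makes global V_T the independent variable in this regression and the symptom and cognition scores the dependent variables. It does not name the other predictors. Neither section says whether the power refers to the whole model or to the V_T coefficient.

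**The concern.** An R² for a whole model with 10 predictors is normally tested with 10 numerator df, and that costs a good deal of power at alpha 0.01. A power above 99% with n = 80 looks too high for it. If the figure instead belongs to one coefficient, then the effect size is mislabelled, and the plan assumes that V_T alone explains what it attributes to the full set of predictors.

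The Aim 1 hypotheses on symptom severity and neurocognition rest on these regressions. With a stated type II risk below 1%, a null result invites the conclusion that there is no association. With a risk of 13%, 19% or more, it does not.

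**Working it through.** **Inputs.** n = 80, p = 10 predictors, two-sided alpha = 0.05/5 = 0.01, R² = .25 (Sample Size Calculation). Pilot partial r = −0.47 and −0.39 at n = 23 (Preliminary studies, item d). Pilot r = 0.82 at n = 5 (item c, repeated in the Sample Size Calculation).

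**Formulas.** f² = R²/(1 − R²); λ = n·f²; error df = n − p − 1 = 80 − 10 − 1 = 69. Power is the probability that a noncentral F with u and 69 df and noncentrality λ exceeds the central F critical value at 0.01. Here u is the number of coefficients tested, and predictors are treated as fixed.

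**1. Reproducing 99.2%.** f² = .25/.75 = 0.333 and λ = 80 × 0.333 = 26.7. Testing one coefficient (u = 1, df 1 and 69) gives **99.3%**, within 0.1 point of the stated figure. Here .25 is the partial R² of that one coefficient.

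**2. The effect size as labelled.** With the same λ but the whole model tested (u = 10, df 10 and 69), power is **81.2%**. Reaching 99.2% on this test would need n of about 136, or an R² of about 0.38 at n = 80. Treating the predictors as random gives 78.8%, and relaxing alpha to 0.05 gives about 94%. Neither reaches the stated figure.

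**3. Overall R² = .25, with V_T explaining part of it.** If V_T's unique share of variance is s, then f² = s/(1 − .25) and λ = 80·s/.75. The shares are assumptions; the documents give none.

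| Unique share s | λ | Power for V_T (df 1, 69) |
|---|---|---|
| 0.05 | 5.3 | 37% |
| 0.10 | 10.7 | 73% |
| 0.15 | 16.0 | 91% |
| 0.20 | 21.3 | 97% |
| 0.25 | 26.7 | 99.3% |

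The last row is the only one that returns the plan's figure. It requires the other predictors to add nothing beyond V_T.

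**4. Is .25 conservative?** Under the coefficient reading, the comparison is with squared partial correlations: 0.47² = 0.221 and 0.39² = 0.152, both below .25.

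- Partial r = 0.47: f² = 0.2209/0.7791 = 0.284, λ = 22.7, power 98.1%.
- Partial r = 0.39: f² = 0.1521/0.8479 = 0.179, λ = 14.4, power 86.9%.

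The one larger cited value, 0.82² = 0.67, comes from 5 people.

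**5. The pilot p-value.** Use t = r·√df/√(1 − r²). For r = −0.39 and n = 23 with no covariates, df = 21, |t| = 1.94 and two-sided p = 0.066. With two covariates, df = 19, |t| = 1.85 and p = 0.081. The protocol prints 0.034.

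**The case against.** The strongest reply is that 99.2% is correct and 81% is beside the point. The text says two-sided, which suits a coefficient test and not an omnibus F test. Section 13 has V_T as the independent variable, and the one-coefficient calculation reproduces the figure almost exactly. Most of this stands. A reader might infer that 81% should simply replace 99.2%, and the documents do not support that, because the coefficient is the more likely target. What does not stand is the effect-size label: .25 is presented as the R² of the overall model, and nothing says that V_T alone accounts for it.

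A reader might also put the pilot values in as overall R², which gives 71.1% at 0.221 and 41.0% at 0.152. That is not like for like. The pilot values are squared partial correlations for V_T, while a 10-predictor R² also includes what the other predictors explain.

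It is fair to add that .25 is well below the 0.67 implied by r = 0.82, so the word conservative has some basis in the text. Five people are weak support for it, and the larger pilot points the other way.

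On the p-value, it is tempting to conclude that a one-sided test was used, since one-sided p at 21 df is 0.033. But item d says covariates were adjusted for, and with two of them one-sided p is 0.040. The companion result (r = −0.47, p = 0.021) lies nearer its two-sided value of 0.024 at 21 df than its one-sided 0.012. The documents show an inconsistency but not its cause, and this p-value does not enter the power calculation.

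Finally, Section 13 does not repeat alpha 0.01 for these regressions. The Sample Size Calculation states it and derives it, so the threshold is not undefined.

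**Conclusion.** The concern holds as a mismatch between the stated effect size and the stated power. With n = 80, 10 predictors and alpha 0.01, an overall R² of .25 has 81% power. The stated 99.2% corresponds to a partial R² of .25 for V_T alone. Both descriptions can be true only if the remaining predictors explain nothing, which the plan does not claim. If they do explain something, power for V_T is lower, by an amount the documents do not determine: from 97% down to 37% over the assumed shares 0.20 to 0.05.

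Taking the n = 23 pilot correlations as V_T's partial effects, power is 98% or 87%, so the type II risk is about 2% or 13% and not 0.8%. The consequence is moderate: the design is not shown to be inadequate, but the near-certainty of detection is not supported by the inputs given. These figures assume a fixed-predictor linear model, all 80 people analysed and the full 10 predictors. The pilot p-value for r = −0.39 does not fit a two-sided test at n = 23.

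**What to change.** In the Sample Size Calculation, name the V_T coefficient as the tested effect, label the effect size as its partial R², and replace the power sentence with:

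> With n = 80, 10 predictors and two-sided alpha 0.01, power for the V_T coefficient is 98% for partial r = 0.47 and 87% for partial r = 0.39; a test of an overall model R² of .25 has 81% power.

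Remove the word conservative. In Preliminary studies, item d, recheck the p-value printed with r = −0.39 against the pilot data and correct whichever figure is wrong.

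The cost is wording and one look at the pilot output. Sample size, procedures and the analysis model are unchanged, but the stated power becomes less favourable.

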### Exclusion criteria:

- Current medical condition such as neurological, cardiovascular, endocrine, renal, liver, or thyroid pathology including COPD, anemia, uncontrolled daily asthma or asthma requiring the use of an inhaler more than 1x/week with an ACT score below 20. A history of vasovagal syncope (fainting) in the last 10 years or any history of unexplained vasovagal syncope will be exclusionary for Aim 2.
- Past or current neurological disorder or disorders affecting the brain including but not limited to multiple sclerosis, history of stroke, brain tumors, traumatic brain injury with loss of consciousness, seizure disorder
- Current drug dependence, current psychotic symptoms and current suicidality, self-injurious behavior or aggressive behavior; MDD and Alcohol Dependence are not exclusionary due to the high comorbidity.
- Current use or regular use of prescription, psychoactive or herbal medications with the exception of marijuana

# Page 16 of 45

(e.g., antipsychotics, anxiolytics, ecstasy, cocaine), with no current drug use confirmed by urine toxicology, which may be associated with inflammation(118). We will not exclude for SSRIs and TRIs due to high prevalence of use within the PTSD population and due to evidence suggesting no effect of these drug classes on endotoxin response (128). Benzodiazepines may not be exclusionary per physician discretion due to high prevalence of use within the PTSD population; dose, history of use, and current frequency of use will be taken into consideration. No subject will be asked to stop taking medication to participate in the study.

- Current or regular use of over-the-counter medication that may affect the immune system (e.g., ibuprofen), including corticosteroids or immunosuppressant drugs; no use 3 days prior to the PET scan
- Vaccination in the last month
- Women who are pregnant or nursing, or fail to use one of the following methods of birth control unless she or partner is surgically sterile or she is postmenopausal (hormone contraceptives [oral, implant, injection, patch, or ring], contraceptive sponge, double barrier [diaphragm or condom plus spermicide], or IUD
- Contraindications to MRI such as claustrophobia or metal in their body
- Individuals who are classified as "low binders" for the rs6971 polymorphism (<10% of the population)
- Subjects whose participation would cause them to exceed yearly radiation limits for research subjects
- Subjects with resting pulse >100 at challenge

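### The power of more than 91.9% claimed for the Aim 2 group difference in LPS response does not follow from its stated inputs, which give about 39% for change scores and about 49% for the planned baseline-adjusted model.

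*Combined protocol and SAP*

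**What the plan says.** The last part of the Sample Size Calculation (Section I, item 4) concerns Aim 2, the PTSD versus control difference in the LPS-induced rise in [11C]PBR28 V_T.

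- **Pilot effect.** From 2 people with PTSD and 2 matched controls it reports "an overall 8.8% difference (d=0.38)in global" V_T values.
- **Effect powered for.** It then proceeds by "assuming a minimum 8.0% differential increase in LPS-induced" V_T in the PTSD group.
- **Other inputs.** Alpha 0.05, "correlation among repeated measures=0.50" and a nonsphericity correction of 1.
- **Claim.** "recruitment of 40 individuals with PTSD and 40 trauma-exposed controls" "will provide greater than 91.9% statistical power to detect this magnitude differential effect size".

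The effect-size index f, the SD of the change, the test and its sidedness are not stated for Aim 2. The Aim 2 part of the Research Plan fixes two scans per subject on one day.

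Statistical Considerations (Section I, item 13) lists first a model of post-LPS global V_T with pre-LPS global V_T as covariate and group and rs6971 genotype as fixed factors. An ANCOVA of percent change follows.

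**The concern.** A standardised difference of 0.38 is modest for 40 per group. At a correlation of 0.50 the SD of a pre-to-post change equals the SD of a single scan, so comparing change between groups is an ordinary two-sample comparison at d = 0.38. Such a comparison cannot have power above 90% with 80 people, so an error in converting the effect size is the natural suspicion.

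Aim 2 is the LPS stress-test hypothesis, and it is the part of the study in which subjects receive endotoxin and a second radiotracer injection. The power statement tells those who approve and later read the study that a true difference of the stated size would be missed fewer than one time in twelve. If that is wrong on the plan's own inputs, a null Aim 2 result could be given more weight than it deserves.

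**Working it through.** **Inputs** (Sample Size Calculation unless noted): N = 80 in two equal groups; m = 2 scans (Research Plan, Aim 2); correlation rho = 0.50; epsilon = 1; alpha = 0.05; d = 0.38. An F test with 1 numerator df is two-sided.

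**1. Reproducing the plan's figure.** For a within-between interaction, lambda = f² × N × m × epsilon / (1 − rho), with 1 and 78 df.
- With f = d/2 = 0.19: lambda = 0.0361 × 80 × 2 / 0.50 = 11.55, power **0.9188**, which rounds to the printed 91.9%.

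The same paragraph's Aim 1 figure (94.2% at d = 0.80) also reproduces with f = d/2 = 0.40: lambda = 0.16 × 80 = 12.8, power 0.9422. There the conversion is valid, because Aim 1 compares two group means.

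**2. The conversion for a difference in change.** If the groups differ by delta in pre-to-post change, each of the four cells carries an interaction effect of ± delta/4. So f = d/4 = 0.095.
- lambda = 0.009025 × 80 × 2 / 0.50 = 2.888, power **0.389**.

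**3. A check that does not use f.** SD of change = SD × √(2(1 − 0.50)) = SD. A two-sample t-test at d = 0.38 with 40 per group has lambda = 0.38² × 40/2 = 2.888, the same value and the same power. A 40,000-replicate simulation gave 0.393. A one-sided test would give 0.516.

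**4. The planned baseline-adjusted model.** Adjusting for the pre-LPS scan reduces the residual variance to (1 − rho²) = 0.75 of that of a single scan.
- lambda = 2.888 / 0.75 = 3.851, with 1 and 77 df, power **0.491**.

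**5. What 8.0% means in SD units.** The plan gives no SD of change, and two readings are available.

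| Reading of 8.0% | Implied SD | d | Change score | Baseline-adjusted | With f = d/2 |
|---|---|---|---|---|---|
| Scaled from the Aim 2 pilot (8.8% / 0.38) | 23.2% | 0.345 | 33% | 42% | 86% |
| Divided by the Aim 1 SD (21.5% / 1.02) | 21.1% | 0.38 | 39% | 49% | 92% |

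**6. What 40 per group can detect at correlation 0.50.** For change scores, 80% power needs d = 0.634, which is 0.634 × 21.1% = 13.4% to 0.634 × 23.2% = 14.7%. With baseline adjustment it needs about 0.634 × √0.75 = 0.55. For change scores, 91.9% power needs d of about 0.76, twice the stated effect.

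**7. Sensitivity to the correlation.** Change-score lambda = 20 × d² / (2(1 − rho)).

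| rho | d = 0.345 | d = 0.38 |
|---|---|---|
| 0.50 | 33% | 39% |
| 0.80 | 67% | 76% |
| 0.90 | 93% | 96% |

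**The case against.** **The doubling is inferred.** The plan prints neither f nor the software, so a reader who takes it as proven that f = d/2 was entered goes beyond the text. This objection stands as to the cause. It does not rescue the figure: every other standard test tried at d = 0.38 and correlation 0.50 gives at most about 52%.

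**The actual power may be far higher than 39%.** This is the strongest counter-argument. Preliminary studies (a) gives a test-retest variability of V_T of 7–9%. If that is a mean absolute percent difference (an assumption), the SD of change without LPS is about 1.25 times as large, 9–11%. Against an SD of 23.2% that implies a correlation of about 0.88–0.93. Variation in the LPS response would add to that SD, so it is a lower bound. The Sample Size Calculation also cites LPS increases of 31% to 63% in 8 healthy subjects. If that is a range across subjects rather than regions, which the text leaves unclear, the SD of change is again about 11%. As illustrations, an SD of change of 14% gives 71–79% power for 8.0–8.8%, and 18% gives 50–58%. A reader might infer from the 39% that the trial will miss a true difference about six times in ten. The documents do not support that as a statement about the trial; it holds only at the assumed correlation of 0.50, for change scores, at d = 0.38.

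**It is unclear what d = 0.38 measures.** The text describes a difference in global V_T between 2 and 2 people and does not say that it is a difference in change. This stands, and it weakens the basis of the stated power further.

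**The Aim 2 sample might be below 80.** The exclusion criteria make syncope history, including "any history of unexplained vasovagal syncope will be exclusionary for Aim 2", exclusionary for this aim alone. It is tempting to infer a smaller sample, but no count is given and the calculation plans 40 per group. Nothing here rests on it.

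**Conclusion.** The Aim 2 power statement is wrong as written. On its own inputs (40 per group, d = 0.38, correlation 0.50, two-sided alpha 0.05), power is about 39% for the interaction or change-score test and about 49% for the baseline-adjusted model, against a claim of more than 91.9%. If 8.0% is scaled from the pilot 8.8%, the values are about 33% and 42%. The best-supported explanation is a between-group effect-size conversion carried into an interaction test. It rests on the match at f = 0.19 and on the Aim 1 figure reproducing with the same conversion.

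The study is not thereby shown to have 39% power, nor to need more subjects. Its power is undetermined until an SD of change, or a justified correlation, is given; figures near 92% would need a correlation of between 0.85 and 0.90 or somewhat above, depending on d and the test. The plan assumes 0.50.

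**What to change.** Withdraw the 91.9% and restate power for the baseline-adjusted model in Statistical Considerations, naming the test, the effect (8.0% or 8.8%), the SD of change and the correlation. Suggested wording on the present inputs:

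> *With 40 per group, correlation 0.50 and two-sided alpha 0.05, power at d = 0.38 is about 49% with adjustment for the pre-LPS scan (about 39% for change scores). For change scores, 80% power needs d of about 0.63, a differential of about 13–15% for an SD of 21–23%.*

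Add the sensitivity to correlation (change-score power about 67–76% at 0.8 and 93–96% at 0.9). If the existing 8-subject pre/post LPS data support a smaller SD of change, recompute from that SD and cite it as the source.

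The cost is one reworded paragraph and, unless a smaller SD of change is documented, a less favourable stated power. No change to enrolment, conduct or analysis is proposed.
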